3.2.5.5. DATA COLLECTION SUMMARY

Time Point	Pre-op ¹	Tx/ Discharge ²	6 wks ³	3 mo ³	6 mo ³	12 mo ³	24 mo ³	Post 24 mo ³
Informed Consent	X							
DDD assessment (MRI, CT or X-ray)	X							
Medical History & Physical Examination	X							
DXA	X							
AP & Lateral X-rays	X	X	X	X	X	X	X	X
Flexion & Extension X-rays	X		X	X	X	X	X	X
Lateral bending X-rays	X				X	X	X	X
MRI (or CT at Pre-op only); Investigational group only at 24M	X							X
Radiographic Core Lab Assessments	X	X	X	X	X	X	X	X
Preoperative Patient Survey	X							
Dysphagia Handicap Index	X		X	X	X	X	X	X
NDI	X		X	X	X	X	X	X
SF-36 Health Survey	X				X	X	X	X
Neck and Arm Pain Questionnaires	X		X	X	X	X	X	X
Foraminal Compression Test	X		X	X	X	X	X	X
Physician Perception of Results			X	X	X	X	X	X
Neurologic Exam	X	X	X	X	X	X	X	X
Gait Assessment	X		X	X	X	X	X	X
Medications	X		X	X	X	X	X	X
Work Status	X		X	X	X	X	X	X
Treatment Assessments		X						
Postoperative Subject Survey			X	X	X	X	X	X
Adverse Event Assessment	N/A				As needed			
Study Completion/ Termination	N/A	N/A			As needed			

a. If indicated as described in Section 3.2.3.3 of this Protocol. b. Made by two Core labs using radiographs.

c. CT acceptable if MRI not available at Pre-op only.

Study windows:

1. Pre-treatment evaluations may be taken up to 6 months prior to surgery; pre-op medications should include medications to the subject is currently taking at the time of the pre-treatment evaluation.
2. Surgery/discharge evaluations must be taken prior to hospital discharge.
3. Follow-up visit evaluations will be taken at 6 weeks (\pm 2 weeks), 3 months (\pm 2 weeks), 6 months (\pm 4 weeks), 12 months (\pm 2 months) and 24 months (\pm 2 months) and annually thereafter. The study visit window for 36 months is (\pm 2 months) visits post 36 months is \pm 3 months.

3.2.6. STATISTICAL CONSIDERATIONS

3.2.6.1. PRIMARY ENDPOINT

The study hypothesis is that in subjects with intractable radiculopathy (arm pain and/or a neurological deficit) with neck pain or myelopathy due to abnormalities localized to the levels of the two contiguous disc spaces at two contiguous levels from C3 to C7 that is unresponsive to conservative management, the Month 24 composite clinical success (CCS) rate of the two-level Simplify Disc will be no worse than conventional two-level ACDF when success is evaluated at Month 24.

Individual success for both the investigational and control groups is defined as:

- Neck Disability Index (NDI) score improvement of at least 15 points from pre-operative;
- Maintenance or improvement in neurological status^{15, 16};
- No serious adverse event classified as implant associated or implant/surgical procedure associated; and
- No additional surgical procedure classified as a “failure.”

Overall success will be determined based on data collected during the initial 24 months of follow-up. Each element of the neurological study exam will be evaluated for maintenance or improvement.

All secondary index surgeries will be classified as failures.

Per FDA Guidance for the Preparation of IDEs for Spinal Systems, the following definitions apply:*

15 Maintenance or improvement in neurological status will be based on motor, sensory, and myelopathic gait assessments.

16 Due to COVID-19, not all 24M visits (entire or portion) are able to occur in-person. If a 24M in-person visit does not occur, the 12M result will be carried forward to represent unavailable 24M results in the primary endpoint and subsequently adjudicated by the CEC.

- Reoperation - any surgical procedure at the index level(s) that *does not involve* modification, addition or removal of any components of the device and is not considered a removal, revision, or supplemental fixation.
- Revision – any procedure in the postoperative or follow-up period that adjusts or in any way modifies either one or both of the original implant configurations (e.g., adjusting the position of the original configuration, removal with replacement with same type of study implant).
- Removal – a procedure that removes one or more components of the original implant configuration without replacement with the same type of trial implant.
- Supplemental fixation – a procedure at the index level(s) in which additional spinal devices not approved as part of the protocol are placed.
- Other – any additional surgical procedure not classified as a removal, revision, supplemental fixation, or reoperation.

3.2.6.2. STUDY SUCCESS

The null hypothesis is that the probability of achieving Month 24 composite clinical success (CCS) for patients implanted with the Simplify Disc device at two levels is no more than 0.10 smaller than the probability of two-level ACDF control patients achieving Month 24 CCS. This study will be considered a success if the 1-sided p-value for rejecting this null hypothesis is less or equal to than 0.05.

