3.2.6.4. SAMPLE SIZE ANALYSIS

The current study is designed to demonstrate non-inferiority using a non-inferiority margin equal to -10.0% at a 1-sided type 1 error rate of $\alpha=0.05$. Subclassification using propensity score (PS) quintiles will be used to minimize selection bias arising from the non-randomized device group comparison. Mantel-Haenszel stratified analyses accounting for PS subclass will utilized when testing the primary non-inferiority hypothesis. A total of 182 two-level investigational subjects will be enrolled and compared to two level ACDF control subjects. The pool of two level ACDF control subjects includes a sample size of N=188. The sample size analyses below demonstrate that these sample sizes are sufficient to test the primary non-inferiority hypothesis after accounting for loss-to-following and PS ‘trimming’ of controls during the observational design phase.

According to Table 28 contained in the [REDACTED] SSED, the overall success was achieved in [REDACTED] controls. Therefore, the control group Month 24 CCS probability was assumed to be 70%. The total control sample size reported in the SSED is N=188. Since selection into a PS sub class will be conducted without access to outcome data, it is assumed that 85% of the selected controls will have a complete Month 24 CCS endpoint. It is also assumed that up to 20% of the controls will be trimmed as part of the PS modeling process. Therefore, for purpose on initial sample size analysis, the control sample size is assumed to be $N = 188 * .85 * .80 = 128$.

It is noted that the 2-level [REDACTED] group experienced an [REDACTED] success rate. For the purpose of sample size analysis, it is assumed that the 2-level Simplify disc

group will have at least a small true superiority margin of 3.5%. That is, it was assumed that the true probability of Month 24 CCS for the investigational group is 75.0%. As noted above, the primary effectiveness hypothesis is non-inferiority with a non-inferiority margin of -0.10 to be tested using at one-sided $\alpha=0.05$. With these assumptions, 154 investigational device patients are required for 80% statistical power as determined using industry standard software (nQuery Advisor 7.0 module PTE0U-1).

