“When the sample sizes in the groups are 128 and 154, a two-group large-sample normal approximation test of proportions with a one-sided 0.050 significance level will have 80% power to reject the null hypothesis that the test and the standard are not equivalent (the difference in proportions, $p_T - p_s$, is -0.100 or farther from zero in the same direction) in favor of the alternative hypothesis that the proportions in the two groups are equivalent, assuming that the expected difference in proportions is 0.035 and the proportion in the standard group is 0.700.”

To account for up to 15% loss-to-follow-up, the total enrolled investigational sample size will be N=182.

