3.2.6.6. NON-INFERIORITY TESTING

The primary non-inferiority test will be conducted using a Mantel-Haenszel stratified analysis approach to pool over PS subclass specific estimated device group differences. If the one-sided p-value for non-inferiority is less than or equal to 0.05, it will be concluded that the two-level Simplify Disc is non-inferior to the two-level ACDF control. In addition to hypothesis testing, the lower bound of a one-sided 95% confidence for the true difference of the device group difference will be determined.

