3.2.6.7. SUPERIORITY TESTING

If the non-inferiority study success criterion is met, superiority testing will be performed in the PE analysis set. It will be concluded that the two-level Simplify Disc is superior to the two-level ACDF control if the one-sided p-value for superiority is less than or equal to 0.025. By the closed testing principal there is no need for a multiplicity adjustment when testing superiority after rejecting the inferiority null hypothesis. Note that 1-sided $\alpha=0.025$ is specified for testing of superiority rather than 0.05 in order to have more definitive evidence to support the stronger claim of superiority.

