missing at random (MAR)³⁰ which is a much weaker assumption than missing completely at random (MCAR) which requires unconditional independence. Although MAR is likely to hold in many more situations than MCAR, in any given situation there is no way to confirm whether the assumption of MAR is tenable and consequently, whether or not the MI analysis produces valid inference. For this reason, a complete case analysis followed by a tipping point sensitivity analysis will be conducted in sensitivity analyses (see below). MI will be used to impute missing final NDI in patients otherwise evaluable for primary CCS. For each imputation, the composite endpoints would be constructed from the imputed NDI values and within randomly completed data sets, the device group difference and standard error is determined. For these imputations, the status of the other CCS components will be based on available data up to the point of loss-to-follow-up which is essentially a last-observation-carried forward approach. In this case, the patient's Month 24 secondary surgical intervention status, major device-related complication status, and neurological success status will be inferred from their Month 12 status. Imputations for NDI will be repeated 20 times to produce 20 randomly completed data sets. The final device group difference will be the average of the multiple imputed datasets and its standard error will account for both within (usual) and between imputation error as described in Rubin and Schenker 1991. The MI standard error will be used in the derivation of the p-value to test the non-inferiority hypothesis. MI analyses will be performed using SAS³¹ Proc MI and MIANALYZE or their equivalent.

A complete case analysis followed by a tipping point analysis will be conducted to complement the primary MI approach in order to evaluate the robustness of statistical conclusions to the assumptions inherent in MI analyses. This includes the untestable assumption; namely, that the probability that a value is missing is independent from the value itself conditional on baseline values and clinical status up to the point. In a tipping point analysis, missing values in each group are separately assumed to be either successes or

³⁰ Rubin DB Inference and missing data. Biometrika 1976, 63:581-592.

³¹ SAS Institute, Cary NC.

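### Section 3.2.6.2 (Study Success) states the non-inferiority null hypothesis in the wrong direction and contradicts the power statement, the decision rule and the superiority section

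*Combined protocol and SAP*

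**What the plan says.** Section 3.2.6.2 (Study Success) sets as the null hypothesis that the Month 24 composite clinical success (CCS) probability for the investigational "Disc device at two levels is no more than 0.10 smaller than the probability of two-level ACDF control patients achieving Month 24 CCS". It continues: "This study will be considered a success if the 1-sided p-value for rejecting this null hypothesis is less or equal to than 0.05".

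Other sections deal with the same test:

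- Section 3.2.2.2 makes lack of clinical inferiority the study hypothesis, with a margin of −0.10.
- Section 3.2.6.4 (Sample Size Analysis) powers the study against a null in which the difference, test minus standard, is minus "0.100 or farther from zero in the same direction".
- Section 3.2.6.6 (Non-Inferiority Testing) begins its rule with "If the one-sided p-value for non-inferiority is less than or equal to 0.05" and concludes that the device is non-inferior in that case. It also asks for a one-sided 95% lower confidence bound for the difference.
- Section 3.2.6.7 (Superiority Testing) opens with "If the non-inferiority study success criterion is met" and says no multiplicity adjustment is needed "when testing superiority after rejecting the inferiority null hypothesis".
- Section 3.2.6.8 adds, for the primary multiple-imputation (MI) analysis: "The MI standard error will be used in the derivation of the p-value to test the non-inferiority hypothesis".

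**The concern.** Write d for P(Simplify) − P(ACDF). To say that Simplify is no more than 0.10 smaller is to say d ≥ −0.10. That is what a non-inferiority trial sets out to show, so it belongs in the alternative. Section 3.2.6.2 puts it in the null and then ties success to rejecting it. Taken literally, the study succeeds only when the data show d below −0.10, that is, when the device is inferior by more than the margin.

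This is the section that formally defines study success, and section 3.2.6.7 makes the superiority test conditional on the study success criterion. The comparison is with a non-randomised historical control, and the plan relies on the design being settled before outcome data are seen. The primary criterion should not have to be inferred by overruling the section that states it.

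**Working it through.** **Direction of the null in each section**

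| Section | Null or rule | In terms of d |
|---|---|---|
| 3.2.6.2 | Null: Simplify at most 0.10 below ACDF; success if rejected | H0: d ≥ −0.10 |
| 3.2.6.4 | Null: −0.10 or further from zero on that side | H0: d ≤ −0.10 |
| 3.2.6.6 | Small p leads to a non-inferiority conclusion; lower bound reported | implies H0: d ≤ −0.10 |
| 3.2.6.7 | The null that is rejected is called the inferiority null | implies H0: d ≤ −0.10 |

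Section 3.2.6.4 is the only other section that spells out the null region. In 3.2.6.6 the direction follows from the conclusion drawn and from the use of a lower bound. In 3.2.6.7 it follows from the name given to the null. The sentence in 3.2.6.8 names no direction.

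**Inputs (section 3.2.6.4):** control rate 0.70; expected difference 0.035, so investigational rate 0.735; 128 control and 154 investigational subjects evaluable; margin −0.10; one-sided alpha 0.05, so z = 1.645.

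**Reproducing the plan's power**

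SE = √(0.735 × 0.265/154 + 0.70 × 0.30/128) = 0.0539

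(0.035 + 0.10)/0.0539 = 2.505

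Power against H0: d ≤ −0.10 is Φ(2.505 − 1.645) = 0.805. The plan states 80%, so its figure is reproduced, and only in this direction.

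**The null as worded in 3.2.6.2**

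Rejecting H0: d ≥ −0.10 requires (observed difference + 0.10)/SE ≤ −1.645. Under the same assumptions the probability is Φ(−1.645 − 2.505) = 0.000017, about 0.002%.

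**The second investigational rate in 3.2.6.4**

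The text also says that the "true probability of Month 24 CCS for the investigational group is 75.0" per cent, which does not equal 70% + 3.5%. That discrepancy is a separate matter and says nothing about the direction of the null; the rate is used here only to show that the result does not depend on it. With 0.75, SE = 0.0535 and 0.15/SE = 2.806. The two probabilities are 87.7% (3.2.6.4 direction) and about 0.0004% (3.2.6.2 wording).

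**What each rule requires of the observed difference (SE 0.0539)**

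- 3.2.6.4 direction: −0.10 + 1.645 × 0.0539 = −0.011, so about −1 point or better.
- 3.2.6.2 wording: −0.10 − 1.645 × 0.0539 = −0.189, so about −19 points or worse.

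For example, an observed +0.035 gives one-sided p = 0.006 in the 3.2.6.4 direction and 0.994 under the 3.2.6.2 wording. An observed −0.20 gives 0.968 and 0.032.

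**Probability of declaring success at other true differences (control 0.70)**

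| True d | Investigational rate | SE | 3.2.6.4 direction | 3.2.6.2 wording |
|---|---|---|---|---|
| −0.05 | 0.65 | 0.0558 | 22.7% | 0.6% |
| −0.10 | 0.60 | 0.0566 | 5.0% | 5.0% |
| −0.25 | 0.45 | 0.0570 | below 0.01% | 83.8% |

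The row at −0.10 is the boundary, where both tests have their nominal 5% error rate. Under the power statement's null, a device exactly at −0.10 still counts as inferior.

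**The case against.** The strongest reply is that this is a drafting slip that would mislead nobody. The study hypothesis, the power statement, the operative rule with its lower bound, and the reference to the inferiority null all agree. Alpha, sidedness and margin are the same throughout, and only one phrase is reversed. On that view the section 3.2.6.6 test is the real criterion, and rejection probabilities for a test nobody intends to run add little.

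Much of this stands. The intended direction is recoverable, and the analysis would probably follow 3.2.6.6. The probabilities size the contradiction and do not forecast how the test will be run. What does not stand is the suggestion that the sentence can therefore be left alone. It is current, unredacted text in the section that defines success, no reading of it yields an inferiority null, and the success rule that follows refers back to it.

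It can also be said that changing a few words would be enough, and that 3.2.6.6 offers the confidence bound only as a supplement to the test. That is fair as to the minimum repair. Stating the bound as an equivalent does not add a second criterion, provided it uses the same standard error and reference distribution as the test.

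**Conclusion.** The concern holds. Section 3.2.6.2 interchanges the null and alternative and conflicts with 3.2.6.4, 3.2.6.6 and 3.2.6.7. Followed literally, it would almost never declare success for a device performing as the plan assumes (about 0.002% at 73.5%, against 80.5% in the intended direction), and it would usually declare success for one 25 points worse than control. The realistic consequence is a contradictory pre-specified success criterion that should be corrected before outcome data are seen.

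The direction of the error follows from the wording alone. The figures rest on an unadjusted, unpooled normal approximation with the plan's rates and evaluable numbers. They do not model the propensity-score (PS) stratification or the MI variance.

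**What to change.** Replace the hypothesis and success rule in section 3.2.6.2 with:

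*H0: P(Simplify) − P(ACDF) ≤ −0.10; H1: P(Simplify) − P(ACDF) > −0.10. The study is a success if H0 is rejected at one-sided p ≤ 0.05. Equivalently, the one-sided 95% lower confidence bound for the PS-stratified difference, computed with the same multiple-imputation standard error and reference distribution as the test, is at or above −0.10.*

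This brings 3.2.6.2 into line with 3.2.6.4, 3.2.6.6 and 3.2.6.7, and with the MI standard error specified in 3.2.6.8. The cost is a wording correction to one short section, with no change to sample size, margin, alpha or data collection.

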3.2.6.3. STUDY DESIGN

The 188 control subjects from [REDACTED]
[REDACTED] will be used to form a valid control group for determining the safety and effectiveness of the Simplify Disc device. Effectiveness comparisons will be performed using sub

classification through propensity score (PS) quintiles (Rosenbaum and Rubin, 1983)¹⁷. This approach directly addresses potential selection bias inherent in non-randomized comparisons.

The PS model will be evaluated according to rigorous criteria (Imbens and Rubin 2015)¹⁸ using a published heuristic (Maislin and Rubin 2010)¹⁹. Applications of this heuristic have been recently published (e.g., Keenan, Maislin, et al 2014²⁰; Arnardottir, Lim, Keenan, Maislin et al 2014²¹; and Pak, Keenan, Jackson, Grandner, Maislin et al 2014²²). The heuristic is designed to identify 5 sub classes in which the groups to be compared share the same multivariate distribution of a comprehensive set of baseline variables. Within each sub class, subjects are therefore equally likely to have received the Simplify Disc or conventional ACDF. The propensity score is the observational study analogue of complete randomization in randomized experiments in the sense that its use is not intended to increase precision but only to eliminate systematic biases in treatment-control comparisons (Rubin 2008)²³. Moreover, the "propensity score technique allows the straightforward assessment [of] whether the treatment groups overlap enough regarding baseline covariates to allow for a sensible treatment comparison" (Yue 2007)²⁴.

The PS sub classes will be formed when the prospective enrollment is completed in the investigational group. The standard implementation of the PS sub classification including iterative 'trimming' of subjects from the extremes of the PS distributions for both the

17 Rosenbaum PR and Rubin DB. The central role of the propensity score in observational studies for causal effects. *Biometrika* 1983a, 70:41-55.

18 Imbens and Rubin D. *Causal Inference in the Social and Biomedical Sciences* Cambridge University Press 2015 (in press)

19 Maislin G and Rubin DB. Design of Non-Randomized Medical Device Trials Based on Sub-Classification Using Propensity Score Quintiles, Topic Contributed Session on Medical Devices. *Proceedings of the Joint Statistical Meetings* 2010, pg 2182-2196.

investigational device and controls in order for the Imbens and Rubin 2015 PS model estimation validity criteria to be met and maximum internal validity of the statistical inference. In response to FDA concerns that trimming of investigational device patients can lead to challenges with regard to labeling, the heuristic described by Maislin and Rubin 2010 has been modified to force retention of all investigational device patients. While it is recognized that this may reduce internal validity of the inference, the modified heuristic maximizes external validity since the investigational device analysis set corresponds exactly to the indicated population. In general, trimming of control patients are allowed given the goal of creating a control population that is as similar as possible to the enrolled investigational device patients. We note, however, that it may not be possible to achieve the desired Rubin criteria while also retaining every investigational device participant due to bias introduced by lack of propensity score overlap which reflects lack of covariate balance. In the case that a final PS designed sample that excludes device participants is required, effectiveness results from non-selected investigational device patients will be summarized separately, compared to those selected for inclusion into a PS subclass, and evaluated in effectiveness sensitivity analyses with implications discussed in the clinical study reports submitted for regulatory review. No matter what, all investigational device patients will be included in safety analyses in order to maximize the external validity of the observed safety profile. Only the baseline data used in the PS design will be summarized for trimmed controls.

It is important to note that the sequential model building process used to identify an analysis data set for which there is adequate covariate balance within subclasses, poses no concern for Type I error inflation. This is because the PS model building process makes no use of outcome data. To avoid bias, no outcome data will be provided to the statistician who will be forming the PS sub classes; and the model identification process will be documented in a series of iterations as described in [Maislin and Rubin 2011]. That is, the sequential model-building heuristic should be viewed as part of the 'design of the observational study'. Here 'design' may be interpreted as "contemplating, collecting, organizing, and analyzing data

that takes place prior to seeing any outcome data (Rubin 2008)²⁵". At its conclusion, verification of balance between device groups within sub class will be done through easily interpretable graphical means.

Given the expected similarity of the populations from which the investigational and control groups will be obtained and the specificity of the clinical indication, it is expected that no more than 20% of the ACDF controls will require trimming. The sample size analysis described below accounts for up to 20% trimming of ACDF. It is assumed that no investigational device patients will be trimmed and so no adjustment for investigational device trimming is included in the sample size analysis. Should there be investigational device trimming, it is expected that the number of investigational device patients requiring trimming will be very small with no appreciable effect on statistical power.

We acknowledge that because the proposed propensity score design can only assess the comparability of the two groups after the prospective enrollment has been completed, there can be significant risk that in the end the data may not be comparable. The sample size determination accounts for up to 20% of the ACDF subjects to be trimmed in the iterative heuristic used to construct PS sub classes that meet Rubin's validity criteria. The risk of insufficient sample sizes due to more than 20% control group trimming can be mitigated by continuing enrollment into one the investigational device group should this be needed to obtain the required sample sizes for 80% power to reject the non-inferiority null hypothesis.

An evaluation of the variable collected in the [REDACTED] study indicate that all component variables necessary to formulate the relevant composite clinical endpoints will be available. Any differences in endpoint evaluation are due to the nature of the difference between artificial discs and fusion procedures. The components of the CCS will be evaluated in the same fashion for the ACDF control as they are to be evaluated for Simplify Disc enhancing comparability of results from the two studies. Although composite clinical success requires a threshold improvement in the Neck Disability Index (NDI), the "NDI is the oldest and most

25 Rubin D. For objective causal inference, design trumps analysis. The Annals of Applied Statistics 2008, 2:3:808-840.

widely used instrument for self-reporting of disability due to neck pain. Its internal psychometric properties have been well established in numerous cultural groups with neck pain: it is highly reliable, strongly internally consistent, and with a 1-factor structure for “physical disability.” It has strong and well-documented convergent and divergent validity with other instruments used in the evaluation of patients and subjects with neck pain” (Vernon 2008)²⁶. The minimum clinically important difference in cervical spine fusion surgery was established to be 15 points out of 100 (Carreon, Glassman and Campbell 2010)²⁷.

Similarly, an evaluation of the baseline variables collected in the [REDACTED] study indicate that a sufficiently rich set of common baseline covariates were collected in both studies. A key exception to this is the baseline pain instrument. The [REDACTED] study utilized a numerical rating scale while the Simplify study was originally designed to use a 100 mm VAS. In order to have comparability with regard to this key baseline covariate and for evaluations during the follow-up period, the Simplify study will now also utilize a numerical rating scale. The very small number of patients enrolled into the Simplify study evaluated with a baseline VAS will be included in the analysis with baseline VAS imputed as missing values as described below.

In summary, the above factors lead to the reasonable expectation that the design of the observational study using PS sub classes will result in statistical estimates of treatment group differences in Month 24 composite clinical with acceptably low bias.

At the conclusion of the PS sub-classification but prior to unblinding the statistician responsible for the PS analysis, results will be distributed to key stakeholder including model building process, summary of optimality criteria, and tabular and graphical summarizes of

26 Vernon H. The Neck Disability Index: State of the Art 1991-2008. Journal of Manipulative and Physiological Therapeutics 2008, September 491-502.

achieved covariate balance. This will include the use of a “Love Plot” (Ahmed et al 2006²⁸) that compares balance before and after application of the PS sub-classification heuristic, adjusting for PS subclasses.

